**Inclusion Criteria:**

A total of 60 subjects are expected to enroll in this trial with a total of 40 completing the study protocol in its entirety to perform statistical analyses on our primary outcomes. We will recruit soccer players between the ages of 13-18 who are healthy, have no underlying metabolic diseases and have no contraindications to exercise.

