### **Procedures performed for research purposes only:**

## **Statistical Methods, Data Analysis and Interpretation**

---

A two-way (group x time) repeated measures analysis of variance (ANOVA) will be used to compare change between groups in body composition, performance, and recovery. If a significance in group x time interactions occur, an independent t-test will be performed for each dependent variable between groups. An alpha level will be set at  $p < 0.05$ .

Sample size and power analysis: For a total of 60 participants, we anticipate a 30% attrition, leaving us with  $n=40$  ( $n=20$  per group). This provides  $>90\%$  power for detecting differences in our main outcome variables. Based on preliminary data, a similar study used  $n=18$  for their sample sizes. This sample size will be used for sample size calculations for a future well-

powered trial. Estimates for effect sizes will be implemented due to the limited sample size. Effect sizes ( $n^2$ ) will be defined as small (0.20), medium (0.50), and large (0.80).

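### The stated power above 90% has no stated basis and cannot be reproduced; with 20 per group, 90% power for a pre-post outcome needs a difference of about 1.05 SD of change

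*Combined protocol and SAP*

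**What the plan says.** In the combined protocol and SAP, under Statistical Methods, Data Analysis and Interpretation, the main test is a group by time repeated-measures ANOVA for body composition, performance and recovery. Independent t-tests follow if the interaction is significant. "An alpha level will be set at" p < 0.05; the number of sides is not given.

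The sample size paragraph then makes these statements:

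- "For a total of 60 participants, we anticipate a 30% attrition", which it takes to leave 40, or 20 per group. The Inclusion Criteria section likewise expects "a total of 40 completing the study protocol in its entirety".
- This number is said to give more than 90% "power for detecting differences in our main outcome variables".
- The supporting sentence begins "Based on preliminary data, a similar study used" and gives n=18. No result from that study is reported.
- The sample is to inform the sizing of a later, adequately powered trial, and "Estimates for effect sizes will be implemented due to the limited sample size".
- Effect sizes, labelled n², "will be defined as small (0.20), medium (0.50), and large (0.80").

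**The concern.** A power figure has meaning only for a given outcome, effect, variability and test. The plan gives one figure for several kinds of outcome and none of these inputs. The size of another study is not a power calculation, because it says nothing about the effect that study could detect or did find.

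The paragraph also pulls in two directions. It claims power above 90% for the main outcomes, yet it calls the sample limited and looks ahead to a trial that would be adequately powered.

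At stake is how a null result is read. If the >90% figure is carried into a report, a non-significant difference could be taken as fair evidence that whey protein does nothing. Nothing in the plan shows that the trial could detect a moderate effect on any particular outcome.

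**Working it through.** **Inputs.** From the Statistical Methods section: alpha 0.05, 20 per group, claimed power >90%, cut-offs 0.20/0.50/0.80. Not given, so assumed or varied: two-sided testing, and the pre-post correlation ρ.

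**The plan's own figure.** It cannot be reproduced, because no effect size or SD is attached to it. The check can only ask what effect the figure would require.

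**Step 1: the test.** With two time points, the group by time interaction is equivalent to a two-sample t-test on the change score. For a difference of d SDs of change and n per group, the noncentrality is d × √(n/2), on 2n − 2 degrees of freedom. With n = 20 this is d × √10 on 38 df, with critical value 2.024.

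| d (SD of change) | Noncentrality | Power, two-sided 0.05 |
|---|---|---|
| 0.20 | 0.63 | 9.5% |
| 0.50 | 1.58 | 33.8% |
| 0.80 | 2.53 | 69.3% |
| 0.909 | 2.87 | 80% |
| 1.052 | 3.33 | 90% |

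Tested one-sided, power at 0.80 is 79.9% and at 0.50 is 46.3%; 90% power then needs 0.94 SD.

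**Step 2: effects in outcome SDs.** With equal SDs before and after, the SD of change is √(2(1 − ρ)) outcome SDs. An effect of δ outcome SDs is therefore δ/√(2(1 − ρ)) SDs of change.

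| ρ (assumed) | Power at δ = 0.5 | Power at δ = 0.8 |
|---|---|---|
| 0.3 | 25.6% | 54.9% |
| 0.5 | 33.8% | 69.3% |
| 0.7 | 51.2% | 88.9% |
| 0.8 | 68.3% | 97.4% |
| 0.9 | 93.1% | >99.9% |

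Setting δ/√(2(1 − ρ)) = 1.052 gives ρ = 1 − (δ/1.052)²/2. For δ = 0.8 this is 1 − 0.289 = 0.71. For δ = 0.5 it is 1 − 0.113 = 0.89.

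**Step 3: the n² label.** The label appears to mean eta-squared, but the cut-offs are the usual ones for a standardised mean difference. For two equal groups, d = 2√(η²/(1 − η²)). Read literally, 0.20, 0.50 and 0.80 are d = 1.0, 2.0 and 4.0, with power 86.9%, >99.9% and >99.9%. Reaching 90% needs η² = 0.217, and 2√(0.217/0.783) = 1.05. The detectable difference is the same under either label.

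**Step 4: attrition.** 60 × 0.70 = 42, or 21 per group. Ending with 40 means losing 20/60 = 33.3%. With 21 per group, power is 71.6% at 0.80 and 35.3% at 0.50, and the detectable differences are 0.89 SD (80%) and 1.03 SD (90%).

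**The case against.** The strongest reply is that the plan's figure has been shown to be unverifiable, not false. The cut-offs are there to classify effect estimates and are not tied to the power statement. They are labelled n², so reading them as standardised mean differences is an inference from their values. The planned test also gains from a high pre-post correlation: above about 0.71, power for 0.8 outcome SD passes 90%. All of this stands, so 69% and 34% must be given with their conditions.

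Two stronger readings are tempting, and the documents support neither.

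- A reader might infer that the trial's true power is 69% at best for a large effect, or that it can detect only very large differences in most outcomes. That would need the effect scale and the correlations, which are not given. Some body composition or performance measures could correlate highly enough; the plan does not say.
- A reader might infer that muscle soreness (DOMS), which is not among the baseline questionnaires, is held to 69% and 34%. Under Intervention, that questionnaire is scheduled at weeks 2, 4, 6, 8, 10 and possibly 12. Averaging five visits multiplies the SD by √((1 + 4r)/5), where r is the between-visit correlation. Power at 0.8 SD is then 96.0%, 88.9% or 76.7% for assumed r of 0.3, 0.5 or 0.8. The two-time-point figures do not carry over to this or the other repeatedly measured outcomes.

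It is also fair that the plan has no rule for interpreting a null result and that Purpose and Objectives speaks of preliminary data, so misreading is a risk and not a certainty. The attrition slip is small and errs on the cautious side.

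None of this supplies a basis for the >90% claim.

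**Conclusion.** The point holds in conditional form: the claim of more than 90% power is unsupported and cannot be reproduced. For a pre-post outcome with 20 per group and two-sided alpha 0.05, it is met only if the true difference is at least 1.05 SD of the change score; 80% power needs 0.91 SD. Power is 69% at 0.80 and 34% at 0.50 if those cut-offs mean standardised differences in change. If they mean outcome SDs, 90% power requires a pre-post correlation of about 0.71 or 0.89 respectively. These results rest on two assumptions that the plan should settle, namely two-sided testing and analysis at two time points; the outcome-SD figures also assume equal SDs before and after.

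The attrition error (42 against 40) is definite, but it moves power at 0.80 only from 69% to 72%.

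**What to change.** Replace the sentence claiming more than 90% power with, for example:

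> With 20 completers per group (33% attrition from 60) and two-sided alpha 0.05, the trial has 80%/90% power for a between-group difference in pre-post change of 0.91/1.05 SD of the change score; power is 69% at 0.8 SD and 34% at 0.5 SD of change. A non-significant result will not be read as absence of effect.

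Alternatively, keep a higher figure, but only for a named outcome with its effect size, SD, pre-post correlation and sidedness stated. If 30% attrition is what is meant, use 42 completers (21 per group) with 0.89/1.03 SD, and align the Inclusion Criteria section.

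In the same paragraph, remove the n=18 precedent as a basis for power and relabel the 0.20/0.50/0.80 cut-offs as standardised mean differences instead of n². Make no power statement for soreness or the other repeatedly measured outcomes without stating how the visits are combined and the between-visit correlation.

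The cost is wording only, with no added participants or procedures. The stated power becomes less favourable.

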
## Purpose and Objectives

---

The overall aim of the proposed project is to compare protein supplementation on performance, recovery, and body composition changes in adolescent soccer players between the whey protein and the control group in response to the 10-week intervention. Hypothesis: We hypothesize that the whey protein group will demonstrate more favorable changes in

performance, recovery, and body composition outcomes than the control group following the 10-week supplementation period.

Secondary outcomes will include investigating interactions between sleep physiology and dietary protein on muscle recovery and performance following the 10-week intervention.

*Hypothesis:* Sleep efficiency will be higher in the whey protein supplementation group versus the placebo control. *Exploratory* analyses will examine the impact of whey protein supplementation on dimensions of sleep including duration, regularity, satisfaction, alertness, timing, and sleep staging (e.g., stage N1, N2, SWS, rapid eye movement (REM))

The **expected outcomes** will provide support for whey protein supplementation to enhance exercise performance, recovery, and body composition in adolescent, team-sport athletes. Completion of the proposed objectives (see below) will add to the sparse evidence base on protein supplementation in this unique, athletic population, and provide preliminary data for future investigations in this area. Specifically, future work could address both mechanistic questions as well as evaluation of other protein options, such as milk consumption, which could be a more cost-effective and acceptable option for youth athletes.

Objective 1: Compare the impact of 10-weeks of whey protein vs. isocaloric control on performance in high school soccer players.

Objective 2: Compare the impact of 10-weeks of whey protein vs. isocaloric control on body composition in high school soccer players.

Objective 3: Compare the impact of 10-weeks of whey protein vs isocaloric control on hunger and satiety in high school soccer players

Objective 4: Compare the impact of 10-weeks of whey protein vs. isocaloric control on sleep duration and quality in high school soccer players.

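### Effect sizes are to be labelled from point estimates with no interval, on a metric that does not fit the cut-points; with 20 per group the labels mislead on either reading

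*Combined protocol and SAP*

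**What the plan says.** All of this is in the combined protocol and SAP, under Statistical Methods, Data Analysis and Interpretation.

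- The main analysis: "A two-way (group x time) repeated measures analysis of variance (ANOVA) will be used to compare change between groups". A significant interaction leads to independent t-tests, with alpha at 0.05.
- The sample: 60 enrolled and 40 analysed, 20 per group, with power above 90% claimed for the main outcome variables.
- The addition prompted by the small sample: "Estimates for effect sizes will be implemented due to the limited sample size".
- The classification: "Effect sizes ( $n^2$ ) will be defined as small (0.20), medium (0.50), and large (0.80".

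The same paragraph refers to sample-size calculations for a later trial. Neither this section nor any other mentions a confidence interval, a standard error or a between-group difference in natural units.

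**The concern.** A small sample is where a point estimate is least reliable, yet the plan's stated response to a small sample is to label point estimates. Without an interval, the reader cannot tell whether a medium effect is distinguishable from zero, or what a null result has excluded.

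The metric adds a second problem. The symbol n² reads as eta squared, a share of variance, while 0.20, 0.50 and 0.80 are on the scale usual for a standardised mean difference. The two readings put the labels in very different places, so the plan does not fix what small or medium will mean.

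Interpretation across the outcomes is at stake, and so is the later trial. A standardised difference of 0.5 carried forward as a planning value implies 64 per group for 80% power (two-sided 0.05). The upper limit of its interval, 1.13, implies about 14 per group, and its lower limit is below zero. Labels alone hide that range.

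**Working it through.** **Inputs from the plan.** 20 analysed per group, alpha 0.05, cut-points 0.20, 0.50 and 0.80, metric printed as n².

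**Assumptions.** Two-sided tests (the plan does not state sidedness). A true effect of zero for the labelling rates. Outcomes measured before and after, so the group by time interaction has 1 and 38 df and its F is the square of the t for the difference in change. On the first reading, standardisation by the SD of the analysed variable.

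**The plan's own figure.** Power above 90% cannot be reproduced or refuted, because no effect size, SD or named main outcome is given. With 20 per group, 90% power needs a standardised difference d of about 1.05; at d = 0.8 power is 69%. Attrition of 30% from 60 leaves 60 × 0.70 = 42, not 40. That hardly matters here: 21 per group gives 52.1% and 11.3% in place of 53.1% and 12.2% below.

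**Reading A: standardised mean difference.** d = t × √(2/20), so under the null P(|d| ≥ c) = 2 × P(t₃₈ ≥ c × √10).

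| Label at least | t needed | Either direction | Favouring whey |
|---|---|---|---|
| small, 0.20 | 0.632 | 53.1% | 26.5% |
| medium, 0.50 | 1.581 | 12.2% | 6.1% |
| large, 0.80 | 2.530 | 1.6% | 0.8% |

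A simulation of 200,000 trials gave 53.0%, 12.2% and 1.6% in either direction.

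The smallest significant d is 2.024 × √0.1 = 0.640. All estimates from 0.20 to 0.50, and those from 0.50 to 0.64, are therefore labelled but not significant.

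Interval for an observed d of 0.5: SE = √(2/20 + 0.5²/80) = 0.321, so 0.5 ± 1.96 × 0.321 = −0.13 to 1.13. For d = 0.20 the same formula gives −0.42 to 0.82.

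*Sensitivity to the standardiser.* If the difference in change is divided by the baseline SD, the rates depend on the pre-post correlation ρ: P = 2 × P(Z ≥ c × √10 / √(2(1 − ρ))), by normal approximation.

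| ρ | at least small | at least medium |
|---|---|---|
| 0.3 | 59% | 18% |
| 0.5 | 53% | 11% |
| 0.7 | 41% | 4% |
| 0.9 | 16% | 0.04% |

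**Reading B: eta squared, as printed.** η² = F/(F + 38), so the F needed for a cut-point c is 38c/(1 − c).

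- Small, 0.20: F = 38 × 0.20/0.80 = 9.5, P = 0.0038, or 0.38%.
- Medium, 0.50: F = 38 × 0.50/0.50 = 38, P ≈ 0.0000003, or about 0.00003%.

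Significance at 0.05 needs F = 2.024² = 4.098, so η² = 4.098/42.098 = 0.097. In d units, √(4.098 × 0.1) = 0.64 and √(9.5 × 0.1) = 0.97. A significant difference between about 0.64 and 0.97 SD would fall below small.

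**The case against.** The strongest objection is that the 53% and 12% depend on a metric the plan does not print. On the printed metric with the printed cut-points, nearly nothing is labelled under the null, and every label belongs to a result that is already significant. This stands. A reader might infer that the labels overstate noise whichever metric is used; the documents do not support that. The direction of the error reverses between the readings, and the large null rates belong to Reading A only.

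A reader might also infer that the labels take the place of hypothesis testing, or will be used to claim benefit without a significant test. The text does not say so. The ANOVA and t-tests at 0.05 remain, with effect sizes added to them. The statement in Purpose and Objectives that the expected outcomes "will provide support for whey protein supplementation to enhance exercise performance, recovery, and body composition" is an expectation and is not tied to the labels.

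Three further limits hold. For a favourable statement about whey, the one-direction rates are the relevant ones, and they are half the totals. The standardiser is unstated and changes the rates greatly. The documents do not fix the number of outcomes, so no probability of at least one misleading label across the set is claimed here.

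The objection does not remove the lack of any interval, or the mismatch between metric and cut-points.

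**Conclusion.** The point holds in a conditional form. The plan labels effect-size point estimates because the sample is limited, plans no measure of their precision, and leaves the metric unclear.

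- **If a standardised mean difference is meant**, labels will often be attached to noise: an expected 53% of null outcomes at least small and 12% at least medium in either direction.
- **If eta squared is meant as printed**, the labels understate: 0.4% of null outcomes reach small and almost none medium, but significant effects with η² from 0.097 to 0.20 rank below small.

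The percentages are expected shares of null outcomes, so they do not require the outcomes to be independent. They rest on 20 per group, two-sided testing and pre-post outcomes; those for Reading A also rest on the choice of standardiser. The main tests are unaffected. The defect lies in how the results will be read and carried into a later trial.

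**What to change.** In Statistical Methods, Data Analysis and Interpretation, replace the two effect-size sentences with wording to this effect:

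*For each outcome, the whey minus control difference in change will be reported in natural units with its 95% confidence interval. Any standardised effect size will be [metric], standardised by [SD], classed by cut-points defined for that metric, and shown with its 95% confidence interval. A size label alone will not be interpreted as evidence of benefit.*

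The sponsor fills in the metric and the standardiser. If a standardised mean difference was intended, the printed cut-points can stay and the n² symbol should go. If eta squared was intended, the cut-points need to be restated for that scale.

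No new data are needed, and the natural-unit intervals come from the models already planned. The cost is slightly more reporting, and some favourable-looking labels will be seen to be uncertain.

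### The effect size is written as n² but graded 0.20/0.50/0.80, the scale of a standardised mean difference, so metric and cut-points do not match

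*Combined protocol and SAP*

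**What the plan says.** All the relevant text is in the combined protocol and SAP, under Statistical Methods, Data Analysis and Interpretation, except that the number of completers also appears under Inclusion Criteria.

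- **Analysis.** A two-way (group by time) "repeated measures analysis of variance (ANOVA) will be used to compare change between groups in body composition, performance, and recovery". If the interaction is significant, "an independent t-test will be performed for each dependent variable between groups". Alpha is 0.05, with sidedness not stated.
- **Effect size.** The plan says that effect sizes will be estimated because the sample is small, and then gives the grading rule: effect sizes, written n², "will be defined as small (0.20), medium (0.50), and large (0.80").
- **Sample.** 60 are enrolled, "with a total of 40 completing the study protocol in its entirety", taken as 20 per group.

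No standardised mean difference is defined anywhere in the document, and nothing elsewhere explains or corrects the cut-points.

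**The concern.** Eta squared is the share of variance attributed to an effect and cannot exceed 1. A standardised mean difference is a number of standard deviations and has no upper limit. The two are on different scales, and cut-points for one do not carry over to the other. The only analysis in the plan that naturally yields a squared effect size is the repeated measures ANOVA, yet the values 0.20, 0.50 and 0.80 are those commonly used for a difference in SD units.

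What is at stake is the wording of the results. The plan turns to effect sizes because the sample is limited, so the grades are likely to be read alongside the p-values. Followed literally, the rule could describe one outcome as a significant interaction and, in the same sentence, as less than a small effect.

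**Working it through.** **Inputs.** From the plan: cut-points 0.20/0.50/0.80, 20 completers per group, alpha 0.05. Assumed: n² is eta squared; a pre/post outcome has two occasions, so the interaction is tested by F(1, 38); the F test corresponds to a two-sided test. Throughout, d is the between-group difference in mean change divided by the SD of the change score.

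**The plan's own figure.** The section claims more than 90% power, but gives no target effect, SD or pre-post correlation, so that figure cannot be reproduced. Nor does it show which metric is meant, because the plan ties it to none of the three grades. With 20 per group and two-sided 0.05, d = 0.2/0.5/0.8 gives power of 9%/34%/69%. Eta squared of 0.20 (d = 1.0) gives 87%, and 0.50 gives over 99.9%.

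**Step 1: convert the cut-points.** For two equal groups the population relation is η² = d²/(d² + 4), with inverse d = 2√[η²/(1 − η²)].

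| Cut-point | Equivalent d if it is η² | Equivalent η² if it is d |
|---|---|---|
| 0.20 | 2√(0.20/0.80) = 1.0 | 0.04/4.04 = 0.010 |
| 0.50 | 2√(0.50/0.50) = 2.0 | 0.25/4.25 = 0.059 |
| 0.80 | 2√(0.80/0.20) = 4.0 | 0.64/4.64 = 0.138 |

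**Step 2: where significance falls.** In the sample, partial η² = F/(F + 38). The critical value is F = 4.098, so p = 0.05 corresponds to 4.098/42.098 = 0.097.

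**Step 3: where the grades begin.** Inverting, F = 38η²/(1 − η²).
- *Small*: 38 × 0.20/0.80 = 9.5, p = 0.0038.
- *Medium*: 38 × 0.50/0.50 = 38, p about 3 × 10⁻⁷.
- *Large*: 38 × 0.80/0.20 = 152, p about 7 × 10⁻¹⁵.

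**Step 4: the band in SD units.** With 20 per group F = 10d², so d = √(F/10).
- Just significant: √0.4098 = 0.64.
- Start of *small*: √0.95 = 0.97.
- Start of *medium*: √3.8 = 1.95.

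So an observed d from 0.64 to 0.97 is significant but below *small*, and one from 0.97 to 1.95 is only *small*. For example, d = 0.8 gives F = 6.4, p = 0.016 and partial η² = 6.4/44.4 = 0.144. That is *large* by the same cut-points read as d, and below *small* read as η².

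**Step 5: how often.** If the true d were 0.8 (illustrative; the plan gives no expected effect), the chance of significance is 69.3% and the chance of being significant with partial η² under 0.20 is 38.5%. Thus 0.385/0.693, about 56% of significant results, would be graded below *small*.

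**Step 6: two sensitivities.**
- *Raw instead of change-score SDs.* With equal variances, d(change) = d(raw)/√[2(1 − r)], where r is the pre-post correlation, which is not given. A raw difference of 0.8 SD has η² of 0.138 at r = 0.5, 0.21 at r = 0.7, 0.29 at r = 0.8 and 0.44 at r = 0.9. From r of about 0.7 it reaches *small*; nowhere in this range does it reach *medium*.
- *More occasions.* Sleep measures and the soreness questionnaire are collected every two weeks. Assuming sphericity, the significance threshold in partial η² falls to about 0.076 with three occasions and 0.056 with six. The gap below 0.20 widens, but the conversion to d in Step 1 no longer applies directly.

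**The case against.** The strongest reply is that this is a slip of notation. The text shows a plain n², not a named statistic, and the same section plans between-group t-tests, for which a standardised difference is a natural companion. On that reading the cut-points are right, one symbol is wrong, and no effect is under-graded. This stands as a real possibility, and the document does not settle it. It changes which half of the sentence needs correcting, not whether it does.

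A second reply is that only adjectives are affected. No test, success criterion or decision in the plan uses the grades, and anyone given the numeric effect size can regrade it. This also stands and limits the weight of the point.

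Three stronger readings are tempting, and the documents do not support them.
- A reader might infer that nearly every plausible effect would be dismissed as negligible. The plan states no expected effect, SD or correlation from which to judge plausibility, and has no negligible grade.
- A reader might infer that all significant effects fall below *small*. With two occasions, results with p below about 0.0038 do reach it.
- A reader might infer that a later trial would be sized wrongly. The plan links its sample size, not the grades, to that trial, and a sample-size calculation uses numbers rather than labels.

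**Conclusion.** The point holds: as written, the metric and its cut-points do not belong together under either reading of the symbol. The under-grading calculated above is conditional on n² being eta squared, 40 completers, two occasions, and differences expressed in change-score SDs. In raw SDs its size depends on a pre-post correlation that the plan does not give. The mismatch itself depends on none of these. Because the tests, p-values and numeric estimates are untouched, this is a minor-to-moderate correction to how results are graded and interpreted, and not a threat to the trial's inference.

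**What to change.** Before any results are seen, name one effect-size metric and give it cut-points that belong to it. Either option resolves the mismatch:

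- a standardised between-group difference in change (d or Hedges g), keeping 0.20/0.50/0.80 and stating which SD is the denominator; or
- partial eta squared for the group-by-time interaction, with about 0.01/0.06/0.14, the rounded equivalents from Step 1.

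A 95% confidence interval alongside the estimate is preferable with a sample this small, but is not needed to correct the mismatch. The cost is one line of wording in the statistical section, with no change to procedures, data collection or tests.
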